7.1.5 Safety committee

Safety committee will not be used in this study.

8. STATISTICAL METHODS AND SAMPLE SIZE

The aim of this hypothesis-generating study is to evaluate the development of puberty in young males with a delayed progress or absent puberty after various testosterone supplementations with or without rhFSH. The primary endpoint of this study is pubertal LH responses on GnRH test at 12 months (group I) and testis size 8 mL or more for young males with a delayed progress puberty (group II). LH ≥ 1 ug/mL is clinically relevant sign that puberty has started and 8mL in testis size relevant for the clinical signs of puberty (growth spurt). The primary endpoint is in both groups a dichotomy response (0/1 yes or no).

The sample size is not formally calculated with consideration to statistical power since Testoviron treatment is SoC today and has not been evaluated.

Since one of the aims in the study is to know if Testoviron treatment can be replaced by Puregon/Nebido in boys with ascents of puberty and by Nebido in boys with delay and slow progression of puberty a bioequivalence analysis and non-inferior interpretation will be performed on primary end points.

Bioequivalence analysis and Non-inferior interpretation: The new treatments will be clinically considered similar if the treatments are in 80 -125 % of the result of Testoviron in each group. Since the result on the primary endpoint cannot be expressed with confidence interval (the result on the primary end point is yes or no), the statistical analysis of the results will be done with Fisher exact chi-square test. Furthermore, accepting a criterion that the difference of numbers of boys becoming pubertal being at the most 25%, and further assuming, that 80% (p2, n=16) boys on the old drug, Testoviron Depot®, will become pubertal: using the normal approximation when calculating the lower 95% level for the difference between p1 (% success for boys on Nebido®) and p2 (80%), the number of boys becoming pubertal on Nebido® must exceed 15." (see Appendix E).

For young males with absence or delayed progress of puberty, the number of subjects (n=30 in Group I and n=40 in Group II) in a parallel-group designed study is considered sufficient for judgments on the primary hypothesis due to clinical experience of treating the present study population with hormone therapy. However, to not expose boys for a new treatment (Nebido and Puregon in group I and Nebido in group II) that is inferior to SoC, a futility test will be performed after 10 evaluable patients in each arm in the groups. This futility analysis can result in stopping the study if the new treatment (Nebido and Puregon in group I and Nebido in group II) is statistically significant inferior or superior, or

continue the study as planned or increase the numbers patients to have a possibility to reach statistical significance.

The primary objective will be studied with non parametric methods Fisher exact chi-square test,

Descriptive statistics, parametric and non parametric tests will be used for the secondary objectives.

Other statistical methods e.g. regression modelling might be used in an exploratory fashion but no formal interference will be made.

Demographics, safety and self-assessed outcomes will be presented by means of descriptive statistics.

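### The 80-125% similarity range puts a ceiling on a success rate: if Testoviron succeeds in fewer than 80%, a better new treatment can be labelled not similar while passing the plan's own non-inferiority criterion, and no rule says which governs

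*SAP*

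**What the plan says.** Section 8 gives the purpose: "Since one of the aims in the study is to know if Testoviron treatment can be replaced by Puregon/Nebido in boys with ascents of puberty", with the parallel question for Nebido alone in boys with delayed puberty. To answer it, "a bioequivalence analysis and non-inferior interpretation will be performed on primary end points". Two criteria follow in one paragraph.

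- **A two-sided ratio range:** "The new treatments will be clinically considered similar if the treatments are in 80 -125 % of the result of Testoviron in each group". No exception is made for results above 125%.
- **A one-sided difference:** "accepting a criterion that the difference of numbers of boys becoming pubertal being at the most 25" per cent, assessed by "using the normal approximation when calculating the lower 95% level for the difference between p1" (new treatment) and p2 (Testoviron). It is illustrated on the premise "further assuming, that 80% (p2, n=16) boys on the old drug, Testoviron Depot®, will become pubertal", which leads to a requirement of more than 15 successes on Nebido. Appendix E tabulates this for 20 boys per arm. This criterion has no upper limit.

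The endpoint is yes/no in both groups, and yes is the desired outcome: a pubertal LH response in group I, a testis size of at least 8 mL in group II. Section 8 also says that Testoviron has not been evaluated, calls the study hypothesis-generating, and names superiority only as a possible outcome of the interim futility analysis.

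**The concern.** A range of 80-125% suits a question where departure in either direction is a fault, as when two formulations should give the same exposure. Whether a new treatment can replace an old one, judged by the share of boys who succeed, is a one-sided question. Doing better is no reason against replacement, yet a literal reading of the range puts a sufficiently better treatment outside *similar*.

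At stake is the reading of the final result. A higher success rate on the new treatment could be reported as failing the plan's only definition of similarity and, from the same data, as non-inferior. With no stated order between the criteria, that choice would be made after the data are seen.

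**Working it through.** **Inputs.** Range 0.80 to 1.25 on the ratio of success rates; margin 25 percentage points on the difference; assumed Testoviron rate 80% (all section 8). Arm sizes 20 (group II) and 15 (group I), from Table 2. True Testoviron rates below 80% are assumptions, since the plan gives none. The range is applied to point estimates, because section 8 says the primary result cannot be given a confidence interval and names none for the ratio.

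**1. The plan's own figure.** Lower limit = (p1 - p2) - z × sqrt[p1(1-p1)/20 + p2(1-p2)/20], compared with -0.25, with p2 = 16/20.

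| New treatment | Standard error | Lower limit, z = 1.96 | Lower limit, z = 1.645 |
|---|---|---|---|
| 16/20 | 0.126491 | -0.248 (pass) | -0.208 (pass) |
| 15/20 | 0.131814 | -0.308 (fail) | -0.267 (fail) |

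The standard errors match Appendix E, and either z gives the stated minimum of 16.

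**2. Where the ceiling can act.** Ceiling = 1.25 × observed Testoviron rate.

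| Testoviron rate | Ceiling for the new treatment |
|---|---|
| 50% | 62.5% |
| 60% | 75% |
| 70% | 87.5% |
| 80% | 100% |

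At 16/20 or 12/15 and above it cannot be exceeded. It can act at 15/20 or fewer, or 11/15 or fewer. If the true rate is exactly 80%, the binomial probability of that is 0.37 for 20 boys and 0.35 for 15.

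**3. The two criteria on the same data.** For 16/20 against 12/20:

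- Ratio = 0.80/0.60 = 1.33, above 1.25, so not similar.
- Difference = 0.20; standard error = sqrt(0.008 + 0.012) = 0.1414; lower limit = 0.20 - 1.96 × 0.1414 = -0.077, above -0.25, so non-inferior.

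The same happens at the smallest counts above the ceiling elsewhere: 19/20 against 15/20 has a lower limit of -0.012, and 13/20 against 10/20 has -0.153. Going through every pair of counts at 20 and at 15 per arm, no result above 125% fails the 25-point criterion when it is calculated from the observed rates (z = 1.96). Above the ceiling the two rules therefore always disagree.

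**4. How often.** P(ratio > 1.25), summing two independent binomials over all pairs of counts:

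| True new v Testoviron | 20 per arm | 15 per arm |
|---|---|---|
| 80% v 80% | 8.0% | 11.6% |
| 90% v 80% | 22.1% | 24.6% |
| 95% v 80% | 31.5% | 31.6% |
| 60% v 60% (assumed) | 19.0% | 21.4% |
| 80% v 60% (assumed) | 59.8% | 58.8% |

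**The case against.** Four points can be made for the plan.

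- **The consequence is not written.** A reader might infer that a result above 125% forbids replacing Testoviron. Section 8 only says what counts as similar, and the same paragraph offers a non-inferiority reading that a better treatment passes. This stands: the range does not by itself deny replacement.
- **A better treatment does not fail both criteria.** It is tempting to say that 14/20 against 10/20 fails both, having a ratio of 1.40 and fewer than 16 successes. But Appendix E derives the 16 with Testoviron fixed at 16/20 and it does not carry over to 10/20. The plan's method on the observed rates gives 0.20 - 1.96 × 0.1517 = -0.097, a pass. This stands too.
- **Exceeding 125% is not proof of superiority.** Fisher's exact test gives p = 0.30 for 16/20 against 12/20. At true rates of 80% against 60% with 20 per arm, 60% of trials exceed the ceiling but only 19% both exceed it and reach p < 0.05. Equal true rates of 60% exceed it in 19%. So these results cannot be called clearly better. It is equally true that a ceiling crossed this often by chance is a poor basis for a label.
- **At the assumed 80% the ceiling is harmless, and the study is hypothesis-generating.** The first half holds only for an observed rate of at least 80%. The second lowers the stakes but does not reconcile the two criteria.

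None of this supplies a rule for which criterion governs, or a reason for an upper limit on a success rate.

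**Conclusion.** The point holds in conditional form. When observed Testoviron success is below 80%, the stated range can label a better-performing new treatment as not similar, the one-sided criterion in the same paragraph calls it non-inferior, and the plan does not rank them. When observed success is 80% or more the ceiling has no effect.

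For true rates of 90% against the plan's assumed 80%, the conflict arises in 22% of trials at 20 per arm and 25% at 15 per arm. For 80% against 60% it arises in 60% and 59%; that lower Testoviron rate is an assumption, plausible only in that the plan describes Testoviron as unevaluated. The figures also assume independent boys, full arms of 20 or 15, and the range read on point estimates.

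**What to change.** In section 8:

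1. Delete the 125% upper limit for the replacement conclusion.
2. State that the one-sided 25-point non-inferiority criterion, calculated from the observed rates in both arms, governs that conclusion.
3. State that a higher success rate on the new treatment counts as not inferior.
4. Report the ratio of success rates with its confidence interval as description only.

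The same text should name the z value. It makes no difference to the count of 16 out of 20, but it can in group I: 12/15 against 12/15 has a standard error of sqrt(2 × 0.16/15) = 0.1461, so the lower limit is -0.286 with z = 1.96 (fail) and -0.240 with z = 1.645 (pass).

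The cost is a short rewording, with no change to data or procedures. What is given up is the two-sided bioequivalence claim, which the replacement question does not need.

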4. SUBJECT POPULATION

A total of 70 young healthy males between 14 and 16 years with clinically verified absent or delayed puberty will be included. The study population will be identified among referrals to the Department of Pediatrics at the NÄL-hospital in Trollhättan and SU/Östra in Göteborg.

Subjects will be divided into 2 main groups; Group I and Group II depending on puberty status. Each group will be sub-divided into treatment groups (Table 2):

Table 2 *Subjects and treatment*

Subjects	Treatment	N
Group I (absent puberty):	1) Testoviron	15
	2) Puregon and Nebido	15
Group II (delayed puberty):	1) Testoviron	20
	2) Nebido	20

Investigator must keep a record of subjects who entered pre-study screening but were never enrolled (subject screening log). Subjects that do not meet the inclusion/exclusion criteria for a study must not be enrolled into the study. Subject population should be selected without bias.

Two groups of boys will be included; Group I with absent puberty and Group II with delayed puberty

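### Section 8 gives a non-inferiority aim to Fisher's exact test on the false ground that a yes/no endpoint has no confidence interval, and leaves conflicting criteria for similarity

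*SAP*

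**What the plan says.** Section 8 makes both primary endpoints yes/no and states that "a bioequivalence analysis and non-inferior interpretation will be performed on primary end points", because one aim is to learn whether the new regimens can replace Testoviron. It then sets out three things.

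- **Range.** The new treatments "will be clinically considered similar if the treatments are in 80 -125 % of the result of Testoviron in each group". No confidence limit is attached.
- **Test.** Fisher's exact test is chosen for this reason: "Since the result on the primary endpoint cannot be expressed with confidence interval (the result on the primary end point is yes or no"). Later in the section: "The primary objective will be studied with non parametric methods Fisher exact chi-square test".
- **Margin and count.** The text goes on, "accepting a criterion that the difference of numbers of boys becoming pubertal being at the most 25%, and further assuming, that 80"% succeed on Testoviron (16 boys), and, "using the normal approximation when calculating the lower 95% level for the difference between p1" and p2, concludes that more than 15 boys must succeed on Nebido. Appendix E tabulates the standard errors with a divisor of 20 and says, in Swedish, that 16 must succeed if the new treatment is not to be regarded as inferior.

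The planned sizes are "n=30 in Group I and n=40 in Group II". By Table 2 in section 4 that is 15 and 20 boys per arm. Section 8 also calls the study hypothesis-generating, gives no power calculation and says that Testoviron has not been evaluated.

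**The concern.** The reason given for the choice of test is wrong, and the sentence after it shows why: a difference between two proportions has a confidence interval, and the plan takes its lower limit. The error matters because it steers a replacement question to a test of equality. A non-significant Fisher test does not show that two treatments are similar, least of all with 15 or 20 boys per arm.

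The criteria beside the test do not repair this. The 80–125% range is worded as sufficient for similarity, the count of 16 as necessary to avoid inferiority, and nothing says which decides. The count is the only rule tied to a confidence limit, but its Testoviron result is assumed, not observed. The wording does not settle whether the count is a requirement or a worked example. As a requirement it ignores the Testoviron arm of the trial itself. As an example it leaves the rule for observed data, and for Group I, to be inferred.

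At stake is the conclusion that Testoviron can be replaced, which would depend on which sentence of section 8 is followed.

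**Working it through.** **Inputs from the plan.** 20 per arm (Group II) and 15 per arm (Group I); assumed Testoviron success p2 = 0.80 (16/20); margin 25%, used in Appendix E on the difference p1 − p2; range 80–125%; lower 95% limit by normal approximation. Sidedness is not stated, so z = 1.96 (two-sided 95%) and z = 1.645 (one-sided) are both shown.

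**1. Reproducing the count.** Lower limit = (p1 − p2) − z·√[p1(1−p1)/20 + p2(1−p2)/20].

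| New v Testoviron, of 20 | Standard error | z = 1.96 | z = 1.645 |
|---|---|---|---|
| 17 v 16 | 0.1199 | −0.185 | −0.147 |
| 16 v 16 | 0.1265 | −0.248 | −0.208 |
| 15 v 16 | 0.1318 | −0.308 | −0.267 |

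Against −0.25, the smallest passing count is 16 with either z, so the plan's figure is right on its own inputs. If 25% meant 25% of 80%, the margin would be 0.25 × 0.80 = 0.20 and the smallest passing count 17.

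**2. Fisher's test when the new treatment is worse by the whole margin.** True rates 0.80 − 0.25 = 0.55 v 0.80, by exact enumeration of two independent binomials:

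| | 20 per arm | 15 per arm |
|---|---|---|
| Fisher not significant (p ≥ 0.05) | 71% | 83% |
| Observed ratio within 0.80–1.25 | 26% | 29% |
| Lower limit on observed data above −0.25, z = 1.96, normal approximation | 3.0% | 2.9% |
| The same, Newcombe interval | 3.2% | 3.5% |

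The nominal error for the last two rows is 2.5%.

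**3. Range against count.** With 16/20 on Testoviron, the range reaches down to 0.80 × 0.80 = 0.64, a shortfall of 16 points, or 0.64 × 20 = 12.8, so 13 boys.

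| New, of 20 | Ratio to 16 | Fisher p | Range | Count of 16 |
|---|---|---|---|---|
| 13 | 0.81 | 0.48 | similar | fails |
| 14 | 0.88 | 0.72 | similar | fails |
| 15 | 0.94 | 1.00 | similar | fails |

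With both true rates at 80% and 20 per arm, the probability that the ratio lies in the range while fewer than 16 succeed is 0.287.

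**4. Count against a limit on the observed data** (20 per arm, z = 1.96).

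- 16 v 18: −0.10 − 1.96 × 0.1118 = −0.319 (Newcombe −0.328). The count passes; the limit fails.
- 15 v 14: 0.05 − 1.96 × 0.1410 = −0.226 (Newcombe −0.218). The count fails; the limit passes.
- Count and normal-approximation limit disagree in 18% of trials at true rates of 80% v 80%, 24% at 70% v 70% and 33% at 80% v 90% (new v Testoviron; assumed rates).
- At 55% v 80% the count is met in 1.9% of trials. At 65% v 90%, also 25 points worse, it is met in 12%, against 3.4% for the limit.

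**5. Group I.** With 15 boys per arm, 16 successes are impossible. Sidedness matters here: 12/15 v 12/15 has standard error √(2 × 0.16/15) = 0.146, so the limit is −0.286 with z = 1.96 (fails 0.25) and −0.240 with z = 1.645 (passes).

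**The case against.** The strongest defence reads the criteria as cumulative: section 8 joins them so that the new treatment might have to satisfy the range and the confidence-limit criterion together. Then 13 to 15 successes meet one condition and fail another, which is no contradiction. Range plus count would be met in only 1.8% of trials at 55% v 80% with 20 per arm, stricter than the interval rule. Nowhere does the plan say that a non-significant Fisher test proves similarity, so 71% and 83% are not error rates of a written rule. The count can be taken as a worked example for Group II: it speaks of assumptions, names Nebido and divides by 20. Appendix E also settles the scale in practice as points. Finally, the study is hypothesis-generating and without a power calculation.

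Part of this stands. The plan is not permissive in Group II if Testoviron truly succeeds in 80%, and the Group I impossibility bites only if the count is a requirement for both groups. The 12% figure needs an assumed 90% Testoviron rate. But the cumulative reading is not what the text says: the range is worded as enough to call treatments similar, the count as needed to avoid inferiority. If the count is only an example, Fisher's test is the only named analysis, and no rule for observed data or for Group I is written. Low power makes it riskier, not safer, to read non-significance as similarity.

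**Conclusion.** The point holds, and section 8 is wrong as written. The premise that a yes/no endpoint cannot have a confidence interval is false and is contradicted in the next sentence. The named test does not address the replacement aim, and the other criteria can return opposite answers on the same data: in 29% of Group II trials when both arms truly succeed in 80%. It must be fixed because the primary conclusion depends on the rule chosen; the exploratory status lowers the stakes but does not remove the contradiction. The arithmetic behind the count of 16 is correct; its fault is in serving as a decision rule.

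These figures take the planned sizes as fixed, leave out the interim look at 10 evaluable patients per arm, and use the plan's 80% and 25 points. Applying 80% to Group I is an assumption, since the plan's calculation covers only 20 per arm.

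**What to change.** - Delete the statement that no confidence interval is possible.
- In each group, judge non-inferiority by a 95% confidence interval for the observed difference in success proportions (new minus Testoviron), with sidedness stated. Conclude it only if the lower limit lies above one margin on one scale. If 25% is kept, say that it means percentage points.
- Name one interval method in advance. The plan's own normal approximation is the smallest change. A score interval such as Newcombe's also serves and does not collapse at the extreme: for 15/15 v 15/15 the normal-approximation limit is 0.000 and Newcombe's is −0.204.
- Drop the 80–125% range or reconcile it with the margin.
- Replace the count of 16 in section 8 and the last line of Appendix E with this rule, or label them as an illustration for 20 per arm and 16/20 on Testoviron.
- Keep Fisher's test for the question of difference in section 1.3, and state that non-significance is not evidence of similarity.

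**Cost.** A protocol amendment with ethics approval (section 9.5), since the primary analysis changes; no added data or visits. The chance of concluding non-inferiority is modest: at 80% in both arms, 25 points and a two-sided 95% interval, it is 54% in Group II and 46% in Group I by the normal approximation, or 53% and 42% by Newcombe. That reflects the sample sizes, and the plan should say so.

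### Section 8 calls 30 and 40 boys sufficient to judge the primary hypothesis, but at the plan's own 25-point limit and 80% rate an equally good treatment would pass only about 54–66% of the time in Group II

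*SAP*

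**What the plan says.** Section 8 of the SAP calls the study hypothesis-generating and states: "The sample size is not formally calculated with consideration to statistical power". It also names as one aim to learn whether Testoviron can be replaced by the new treatments, and plans a bioequivalence analysis and a non-inferiority reading on the primary endpoints of both groups.

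Two criteria follow.

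- Similarity: the new treatments count as similar "if the treatments are in 80 -125 % of the result of Testoviron in each group". The same paragraph says that a yes/no endpoint cannot be given a confidence interval.
- Non-inferiority: the permitted difference is 25%, "assuming, that 80% (p2, n=16) boys on the old drug" become pubertal, and the limit is found "using the normal approximation when calculating the lower 95% level for the difference between p1" and p2. The conclusion is that "the number of boys becoming pubertal on Nebido® must exceed 15".

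Appendix E works this out for 20 boys per arm. It concludes that 16 boys must succeed if the new treatment is not to be regarded as inferior. It gives no probability of reaching that number and nothing for 15 per arm.

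Section 8 then says that "the number of subjects (n=30 in Group I and n=40 in Group II") "is considered sufficient for judgments on the primary hypothesis due to clinical experience of treating the present study population".

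**The concern.** Having disclaimed a sample-size calculation, the plan sets a pass/fail limit for replacing standard of care and then asserts that the numbers suffice to judge by it. The only support offered is clinical experience. That may inform the expected success rate, but it cannot show how often a sample of this size will clear a confidence limit. The plan's own inputs allow that chance to be computed.

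At stake is how a missed limit will be read. Under Appendix E a new treatment that does not reach 16 successes is regarded as inferior. If a treatment exactly as good as Testoviron often falls short, that label will often be wrong, and nothing in the plan warns the reader of it.

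**Working it through.** **Inputs.** Success on Testoviron 80% and limit 25 points (section 8); 20 per arm in Group II and 15 per arm in Group I (Table 2); lower 95% level by normal approximation, sidedness not stated (section 8), so z = 1.96 and z = 1.645 are both used. The plan gives no expected rate for the new treatment; 80% is taken as the case of equality. No dropout is applied, and the sample sizes are fixed.

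**1. The plan's own figure.** Lower limit = p1 − p2 − z·√[p1(1−p1)/n + p2(1−p2)/n], to lie above −0.25. With p2 = 16/20:

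| New treatment | Standard error | z = 1.96 | z = 1.645 |
|---|---|---|---|
| 16/20 | 0.1265 | −0.248, passes | −0.208, passes |
| 15/20 | 0.1318 | −0.308, fails | −0.267, fails |

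The standard errors match Appendix E and the threshold of 16 reproduces under both values of z. The appendix is arithmetically right.

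**2. Chance of passing under equality, Group II.**

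- Printed rule: P(Bin(20, 0.8) ≥ 16) = 0.630, so it fails 1 − 0.630 = 37% of the time.
- Limit applied with the observed Testoviron rate, by exact enumeration over two independent binomials: 0.543 (z = 1.96) and 0.662 (z = 1.645).
- Rough check: Φ(0.25/√(0.32/20) − z) = 0.507 and 0.630.

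**3. Group I, assuming the same 80% and 25 points.**

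- Exact enumeration, 15 per arm: 0.461 (z = 1.96) and 0.578 (z = 1.645). Rough check: 0.402 and 0.527.
- Identical results of 12/15 and 12/15 give a lower limit of −0.286 at z = 1.96, which fails, and −0.240 at z = 1.645, which passes.
- With Testoviron held at 12/15, the two-sided level therefore needs 13 successes (probability 0.398) and the one-sided level needs 12 (0.648).

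**4. Sensitivity to the common success rate** (exact, observed Testoviron rate):

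| Both arms at | 20 per arm, 1.96 / 1.645 | 15 per arm, 1.96 / 1.645 |
|---|---|---|
| 70% | 44% / 56% | 34% / 46% |
| 80% | 54% / 66% | 46% / 58% |
| 90% | 75% / 82% | 68% / 79% |

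For scale, an 80% chance of passing at 80% success needs 2·0.16·(1.96 + 0.842)²/0.25² ≈ 41 per arm, or 32 with 1.645.

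**5. The 80–125% criterion**, both arms at 80%.

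- Read as an observed ratio: it passes 84% (20 per arm) and 77% (15 per arm). A treatment truly at 55% against 80% would also pass 26% and 29% of the time.
- Read as a 90% interval for the ratio: identical 16/20 results give exp(±1.645·√(2·0.2/16)) = 0.77 to 1.30, and identical 12/15 results give 0.74 to 1.35. Both fall outside 0.80–1.25. The pass rates are 8% and 3%.

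**The case against.** **The plan is candid.** It calls itself hypothesis-generating, admits that no power calculation was made, and rests sufficiency on clinical experience. No printed number is wrong. All of this stands, and it makes the fault an unsupported statement rather than a miscalculation. It does not rescue the statement, because the same section sets a decision limit and Appendix E attaches the word inferior to missing it.

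**The outcome is not simply a coin toss.** A reader might infer that from the 54% and 46%. Those figures use the two-sided level. The printed rule passes 63%, and the one-sided level gives 66% and 58%. Since the plan does not fix the sidedness, the range should be stated.

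**Equivalence is not shown to be almost unreachable.** A reader might infer it from the 8% and 3%, but these need a 90% ratio interval that the plan never attaches to 80–125%; indeed it says that no interval can be given. As an observed ratio the criterion is usually met under equality. What can be said is that the criterion is undefined.

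**Group I is an extrapolation.** The worked rule names Nebido and a denominator of 20. The plan gives no success rate or threshold for the LH endpoint. Section 8 does extend the non-inferiority reading to the primary endpoints of both groups, so the calculation is reasonable, but it remains an assumption.

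**There is an interim look.** Sections 3.1.1, 3.2 and 8 allow stopping or enlargement after 10 evaluable boys per arm. The fixed-sample pass rates are therefore not the full operating characteristics of the design. That option has no stated rule or target size, so it does not support sufficiency either, but any figures written into the plan must say that they leave it out.

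**Conclusion.** The point holds for non-inferiority. On the plan's own limit and its own 80% rate, with fixed samples, an equally good treatment fails in Group II between 34% (one-sided) and 46% (two-sided) of the time, and 37% of the time under the printed rule. On the same assumptions carried over to Group I, it fails 42% to 54% of the time. A sample with these properties cannot be called sufficient for the judgment, and a missed limit cannot be taken as evidence of inferiority.

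The size depends on the true rate: the pass rates are lower if both arms are nearer 70% and higher near 90%. Losses to follow-up would lower them. For 80–125% the conclusion is only that the criterion needs a definition.

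**What to change.** Three linked changes are needed, because altering the sufficiency sentence alone would leave it in conflict with the rest.

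1. In section 8, replace the sufficiency sentence with a statement such as: *The study is hypothesis-generating and is not sized for non-inferiority or equivalence. With 80% true success in both arms and a 25-point limit, the chance of meeting the limit is 54% in Group II with a two-sided 95% level and 66% with a one-sided level (63% for 16 or more of 20). If the same rate and limit are assumed for Group I, it is 46% and 58%. These figures take fixed sample sizes and leave out the interim option to stop or enlarge.* Name which level will be used.
2. In section 8, delete the statement that the result cannot be expressed with a confidence interval, and report the difference in proportions with a 95% confidence interval in each group. State whether 80–125% refers to an observed ratio or to an interval.
3. In section 8 and Appendix E, say that missing the limit means non-inferiority has not been shown, not that the new treatment is inferior.

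The cost is wording in two places and a less favourable statement of adequacy. No extra boys, visits or data are needed.
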